### BACKGROUND AND OBJECTIVES

On average, 8% of the US population gets sick from flu each flu season (Tokars et al. 2018). Since 2010, the annual disease burden of influenza has included 9-45 million illnesses, 140,000-810,000 hospitalizations, and 12,000-61,000 deaths (CDC 2020). The CDC recommends the flu vaccination to everyone aged 6+ months, with rare exception; almost anyone can benefit from the vaccine, which can reduce illnesses, missed work, hospitalizations, and death (CDC 2019). Flu vaccination will be especially important for high-risk patients during the COVID-19 pandemic so that flu cases are reduced and resources conserved.

While most recover from influenza without treatment, the elderly, those with comorbidities, and other high-risk individuals can experience complications such as pneumonia, other respiratory illness, and death. Geisinger has partnered with Medial EarlySign (Medial; www.earlysign.com) to develop a machine learning (ML) algorithm to identify patients at risk for serious (moderate to severe) flu-associated complications on the basis of their existing electronic health record (EHR) data. The development of this algorithm was already approved through a separate Geisinger IRB application (IRB number 2020-0211). Geisinger will deploy this system during the 2020-21 flu season and contact the identified patients with special messages (in addition to standard efforts made by the health system every flu season) to encourage vaccination.

However, there is little evidence about (a) whether informing patients they are at high risk makes them more likely to receive vaccination; (b) how patients react to being told their risk status is the result of an analysis of their health records; and (c) whether informing patients their risk status has been determined by an "algorithm," by "machine learning," and/or by "artificial intelligence" (AI) will increase or decrease their likelihood of getting vaccinated. This study will address these gaps in the literature, which are especially important in light of the anticipated future growth of AI/ML system use throughout healthcare.

Medial's algorithm is an example of how interoperable health information exchange (HIE)—the ability for health information technology to share patient data—can improve the efficiency and effectiveness of healthcare. However, patients may not appreciate these benefits or the fact that healthcare has become substantially more integrated and collaborative. A systematic review of patient privacy concerns about HIE found that 15-74% of patients expressed privacy concerns,

IRB NUMBER: 2020-0290 IRB Approved: 09/13/2021

depending on the study, and concluded that patient perspectives remain poorly understood. A flu outreach message that explicitly references a review of patient medical records might backfire as patients react poorly to a sense they have lost control of their health records, even though in this case the use is intended to benefit their care.

There is conflicting evidence on how people respond to advice or information that comes from an algorithm or machine. Dietvorst et al. (2015) documented a pattern of "algorithm aversion," in which people choose inferior human over superior algorithmic forecasts, especially after they observed the algorithm make an error. In contrast, Logg et al. (2018) described "algorithm appreciation," in which people followed advice more when they thought it came from algorithms than when they thought it came from human beings. Finally, Bigman and Gray (2019) found aversion to algorithms that make "moral decisions," including a (fictitious) medical decision of choosing whether or not to operate on a high-risk patient. In this study, the algorithm is merely advising patients on taking a low-risk action (an annual flu shot) that is already the standard of care and heavily encouraged by Geisinger for all patients (except, of course, those for whom the vaccine is contraindicated), and there is no opportunity to observe an erroneous recommendation, so the hypothesis is that "algorithm appreciation" will cause people to react positively to being informed of the algorithm's role. Thus, this study will address two important research questions:

- 1. Does informing patients that they are at high risk for flu complications (a) increase the likelihood that they will receive flu vaccine; and (b) decrease the likelihood that they receive diagnoses of flu and/or flu-like symptoms in the ensuing flu season?
- 2. Does informing patients that their high-risk status was determined (a) by analyzing their medical records (vs. by no specified method); and (b) by an AI/ML algorithm¹ analyzing their medical records (as opposed to via unspecified methods or human medical records analysis) affect the likelihood that they receive the flu vaccine and/or diagnoses of flu and/or flu-like symptoms in the ensuing flu season?

## Our specific aims are:

- 1. Evaluate the effect on flu vaccination rates of informing health-system patients who are identified by an ML analysis of EHR data to be at high-risk for flu complications that they are at high risk with either (a) no additional explanation, (b) an explanation that this determination comes from an analysis of their medical records, and (c) the additional explanation that an AI or ML algorithm made this determination.
- 2. Evaluate the effects of the same three interventions on diagnoses of flu in the same patients.

.

<sup>1 The study will not necessarily use the terms "AI," "ML," or "algorithm" in the messages; instead, these messages will be designed to be readable and comprehensible by the patient audience while still including the key concepts that differentiate the interventions from one another.

### **PROCEDURES**

# **Research Design**

Patients from the high-risk sample (primary target population) will be randomly assigned to one of 4 study arms. Outcomes during the 2020-2021 flu season will be compared between study arms

## **Study Population**

There are 3 separate populations to consider in the current study: the primary target population that will be randomized into an experimental condition and potentially contacted, and two secondary populations who will not experience an intervention and will only be included for data analysis purposes.

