## 2) Secondary population A (data analysis only): Household members

#### *Inclusion Criteria:*

- Household members of primary target population
- Have data in Geisinger's electronic health records

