### Exclusion Criteria:

• Same as primary target population

> **Recruitment and Enrollment.** All patients meeting the primary target population criteria will be enrolled into one of the 4 experimental conditions. Anticipated enrollment number for this primary target population is 56,000. Only patients from this primary target population will be contacted. However, health record data will be accessed to assess secondary outcomes for household members of this target population (expected N of 234,000) and for patients whose risk scores were calculated by Medial's ML algorithm and determined to fall just below the high-risk cutoff (expected N of 56,000). This brings the total planned enrollment to 346,000 participants.

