## **Detailed Study Procedures.**

Eligible patients will be randomly assigned to one of 4 experimental conditions:

- 1. **Control**: In this condition, patients will receive no additional pro-vaccination intervention beyond Geisinger's normal efforts. Note that these efforts include a variety of Marketing and other system campaigns designed to encourage all patients and members to get their flu shot. In addition, the care gaps team has an annual campaign to encourage flu shots that targets patients who are determined by a non-ML assessment that they are at high risk for complications and we expect there to be overlap between this group of patients and the ML high-risk group we will be contacting. (Because the care gap team's high-risk patients are not told that they are at high risk or that they have been targeted, we are not concerned that this ongoing campaign will interfere with our ability to measure the effects of high-risk communication.)
- 2. **High Risk Only**: In this condition, patients will receive messages telling them they are at high risk for flu complications without specifying how/why Geisinger believes this to be the case.
- 3. **High Risk Based on Medical Records**: In this condition, patients will receive messages telling them they have been identified to be at high risk for flu complications via analysis or review of their medical records. This is an accurate statement, since it does not specify that a human conducted this review or analysis. However, we anticipate that most readers will assume it was a human rather than an algorithm, allowing us to compare attitudes towards human versus machine risk determination.
- 4. **High Risk Based on Algorithm**: In this condition, patients will receive messages telling them they have been identified to be at high risk for flu complications via analysis of their medical records by AI/ML.

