Because this intervention is timed to the 2020–21 flu season, the intervention period will begin ~9/1/20 and last for three months. During that period, all identified primary target population participants will be randomized and will receive 1–3 separate messages (content based on their assigned condition) in sequence via postal letter, SMS, and patient portal modalities, using all modalities available for each participant. Outcomes will be measured as of 5/31/21. Data extraction from the EHR, data cleaning, data analysis, and manuscript preparation will begin on or after 6/1/21 and will include data from not only the primary target population but also the two secondary populations.

> The primary study outcomes will be the rates of flu vaccination and flu diagnoses during the 2020–21 season (start of intervention through 5/31/21) by the primary target population. We will also measure secondary, exploratory outcomes: Rates of flu vaccination and diagnoses by fellow household members of targeted patients; rates of flu vaccination and diagnoses by non-targeted patients who were assigned a risk score that fell just below the cutoff of targeted patients; rates of flu complications and flu-like symptoms among targeted patients, household members, and those at sub-threshold risk; and rates of other relevant healthcare utilization outcomes such as ER visits and hospitalizations.

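### The household-member population does not exclude co-residents who are themselves randomised, and a member living with targeted patients in different arms has no defined arm

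*Protocol*

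**What the plan says.** The protocol's Study Population section opens with "There are 3 separate populations to consider in the current study" and describes the last two as "two secondary populations who will not experience an intervention and will only be included for data analysis purposes".

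Secondary population A has two inclusion criteria, "Household members of primary target population" and "Have data in Geisinger's electronic health records". It has no exclusion criteria. Population B, by contrast, is separated from the targets by risk score and has its own exclusions.

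Under Recruitment and Enrollment, "All patients meeting the primary target population criteria will be enrolled into one of the 4 experimental conditions". The expected numbers are 56,000 targeted patients, 234,000 household members and 56,000 sub-threshold patients, added to 346,000. Only the primary target population is to be contacted. Assignment is by patient: "Eligible patients will be randomly assigned to one of 4 experimental conditions".

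The secondary, exploratory outcomes in Detailed Study Procedures include "Rates of flu vaccination and diagnoses by fellow household members of targeted patients". The SAP's Secondary Analyses section sends the secondary outcomes listed in the pre-registration through Analyses 1 and 2. The SAP considers clustering by primary care provider or clinic, but not by household. Its exclusions concern deceased and already vaccinated patients, not shared households.

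**The concern.** As written, two eligible high-risk people at one address are both randomised, and each also qualifies as a household member of the other. That conflicts with the statements that the populations are separate and that household members receive no intervention. It also means that 346,000 need not be a count of distinct people.

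The larger problem is analytic. Analyses 1 and 2 need one arm per person. Neither document says which arm applies to a household member who lives with targeted patients in different arms. Neither says whether a member who was also randomised is analysed under their own arm or the relative's. Without a rule, analysts would choose after the data are in hand. People vaccinated because of their own message would also be counted in a rate meant to describe spread within the home.

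**Working it through.** **Reproducing the plan's total.** 56,000 + 234,000 + 56,000 = 346,000, which agrees exactly. It counts distinct people only if no targeted patient is also a household member of another target.

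**Which household members have a defined arm?**
- Not targeted, one target in the home: the target's arm.
- Not targeted, two targets in the same arm: that arm, with a double exposure.
- Not targeted, two targets in different arms: no arm is defined.
- Targeted, living with another target: own arm or relative's arm, not stated.

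The documents give no allocation ratio. Assuming equal allocation and independent assignment, two targets in one home fall in different arms with probability 1 − 4 × (1/4)² = 75%. One is messaged and the other is a control with probability 2 × 1/4 × 3/4 = 37.5%. In such homes an undefined arm is therefore common.

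**People counted twice.** Let q be the share of the 234,000 who are themselves targeted. The documents do not give q. The SAP's Question 3 describes the target group as the top 10% of risk, but that is a risk rank, not the chance that a co-resident is a target. The chance is lower where co-residents are under 17, who are ineligible, and higher if risk clusters within homes.
- q = 5%: 0.05 × 234,000 = 11,700 counted twice; 346,000 − 11,700 = 334,300 distinct.
- q = 10%: 23,400 counted twice; 322,600 distinct.
- q = 20%: 46,800 counted twice; 299,200 distinct.

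If the 234,000 was already net of targeted patients, the double count is zero.

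**Controls living with a messaged patient.** With M co-residents, equal allocation and independence, the share is 1 − (1 − 0.75q)^M. At q = 10%:
- M = 1: 7.5%.
- M = 2: 1 − 0.925² = 14.4%.
- M = 234,000/56,000 = 4.18: 1 − 0.925^4.18 = 27.8%.

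The last is an upper-end value. The formula is concave in M, so putting in the mean overstates the share when household size varies. The ratio of two totals is also only a rough stand-in for co-residents per patient.

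**Effect on the primary contrast.** Let d be the direct effect of a message, s the spillover as a fraction of d, and e the share of patients with a messaged co-resident. Because arms are assigned independently, e is the same in every arm in expectation.
- Additive spillover: (d + e·s·d) − e·s·d = d. There is no bias.
- Spillover that adds nothing for a patient already messaged: d − e·s·d = d(1 − e·s). With e from 7.5% to 27.8% and an assumed s of 10% to 50%, attenuation runs from 0.75% to 13.9%.

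Both e and s are assumptions, so this shows the direction and the condition, not an estimate.

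**The case against.** The strongest reply is that the protocol clearly intends separate populations. It calls them separate, says that only targets are contacted, and adds the numbers as if disjoint. On that reading, the household criteria merely fail to repeat an implied exclusion, and no overlap has been shown. This is fair as far as it goes: the documents give no count of shared households. It does not settle the matter, because the criteria as written admit co-resident targets. Even with the exclusion implied, an untargeted person living with two targets in different arms still has no arm.

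A second reply is that the household outcome is exploratory, and that the pre-registration to which the SAP refers may contain household rules. Both points stand. The gap can be asserted only for these two documents.

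A reader might also infer that the control arm is contaminated and the primary results biased. The documents do not support that. Exposure to a messaged co-resident arises from individual randomisation, not from the household criteria, and would remain if the household population were dropped. It is balanced across arms in expectation and matters only if spillover is less than additive. No passage shows that any control saw a message.

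Nor does it follow that the household outcome can say nothing about spread. Members' own messages are also balanced across the index patient's arm in expectation. They blur raw rates and may dilute contrasts, but they do not make the question unanswerable where the arm is defined.

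**Conclusion.** The household criteria conflict with the statements that the populations are separate and that household members receive no intervention, and the household analysis lacks a rule for members linked to more than one arm. This is a real but limited defect in an exploratory outcome. Its size is unknown: the counts above rest on an assumed share of targeted household members, and the exposure figures of 7.5% to at most about 28% of controls rest in addition on equal allocation, independence and an assumed household size.

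Bias in Analyses 1 and 2 for the primary outcomes is not shown. Attenuation is possible under less-than-additive spillover, by an amount that the documents cannot fix. It deserves a sensitivity analysis, particularly for the wording contrasts among groups 2, 3 and 4, where some dilution could contribute to a null result.

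**What to change.** 1. In the protocol, add to secondary population A an exclusion for members of the primary target population, and restate 346,000 as a number of distinct persons.
2. In the SAP, run the household-member analysis by arm only in households with exactly one targeted patient, so that every member has a single arm.
3. In the SAP, add a prespecified sensitivity version of Analyses 1 and 2 restricted to patients who are the only target in their household.

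For items 2 and 3, define households from address data recorded before randomisation. The documents do not say how or when households are linked, and Data Sources has outcome data for all three populations obtained after the intervention. The restriction preserves the randomised comparison only if household membership cannot depend on later events.

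All three changes can be made after the messages have been sent, and the household outcome already requires linkage. The cost is wording, fewer records in the household analysis, and a sensitivity analysis that is less precise and covers a somewhat different population.

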# 1) Primary target population

#### *Inclusion Criteria:*

- Aged 17 or older
- Have been determined as high-risk through Medial's ML algorithm

#### Exclusion Criteria:

- Has contraindications for flu vaccination
- Note: we will respect opt-out communication preferences, but will include patients in the study if they haven't opted out of at least one communication modality employed

## 2) Secondary population A (data analysis only): Household members

#### *Inclusion Criteria:*

- Household members of primary target population
- Have data in Geisinger's electronic health records

## 3) Secondary population B (data analysis only): Sub-threshold risk

#### *Inclusion Criteria:*

• Same as primary target population, except that these patients' algorithmic risk scores fall just below the high-risk cutoff

### Exclusion Criteria:

• Same as primary target population

> **Recruitment and Enrollment.** All patients meeting the primary target population criteria will be enrolled into one of the 4 experimental conditions. Anticipated enrollment number for this primary target population is 56,000. Only patients from this primary target population will be contacted. However, health record data will be accessed to assess secondary outcomes for household members of this target population (expected N of 234,000) and for patients whose risk scores were calculated by Medial's ML algorithm and determined to fall just below the high-risk cutoff (expected N of 56,000). This brings the total planned enrollment to 346,000 participants.

## **Detailed Study Procedures.**

Eligible patients will be randomly assigned to one of 4 experimental conditions:

- 1. **Control**: In this condition, patients will receive no additional pro-vaccination intervention beyond Geisinger's normal efforts. Note that these efforts include a variety of Marketing and other system campaigns designed to encourage all patients and members to get their flu shot. In addition, the care gaps team has an annual campaign to encourage flu shots that targets patients who are determined by a non-ML assessment that they are at high risk for complications and we expect there to be overlap between this group of patients and the ML high-risk group we will be contacting. (Because the care gap team's high-risk patients are not told that they are at high risk or that they have been targeted, we are not concerned that this ongoing campaign will interfere with our ability to measure the effects of high-risk communication.)
- 2. **High Risk Only**: In this condition, patients will receive messages telling them they are at high risk for flu complications without specifying how/why Geisinger believes this to be the case.
- 3. **High Risk Based on Medical Records**: In this condition, patients will receive messages telling them they have been identified to be at high risk for flu complications via analysis or review of their medical records. This is an accurate statement, since it does not specify that a human conducted this review or analysis. However, we anticipate that most readers will assume it was a human rather than an algorithm, allowing us to compare attitudes towards human versus machine risk determination.
- 4. **High Risk Based on Algorithm**: In this condition, patients will receive messages telling them they have been identified to be at high risk for flu complications via analysis of their medical records by AI/ML.

Because this intervention is timed to the 2020–21 flu season, the intervention period will begin ~9/1/20 and last for three months. During that period, all identified primary target population participants will be randomized and will receive 1–3 separate messages (content based on their assigned condition) in sequence via postal letter, SMS, and patient portal modalities, using all modalities available for each participant. Outcomes will be measured as of 5/31/21. Data extraction from the EHR, data cleaning, data analysis, and manuscript preparation will begin on or after 6/1/21 and will include data from not only the primary target population but also the two secondary populations.

> The primary study outcomes will be the rates of flu vaccination and flu diagnoses during the 2020–21 season (start of intervention through 5/31/21) by the primary target population. We will also measure secondary, exploratory outcomes: Rates of flu vaccination and diagnoses by fellow household members of targeted patients; rates of flu vaccination and diagnoses by non-targeted patients who were assigned a risk score that fell just below the cutoff of targeted patients; rates of flu complications and flu-like symptoms among targeted patients, household members, and those at sub-threshold risk; and rates of other relevant healthcare utilization outcomes such as ER visits and hospitalizations.

